## **PROTOCOL**

We will implement the adaptive social VR game and determine the optimal dose. After we construct each subject's affective model with the machine-learning algorithm, we will test the effects of the adaptive VR games in 40 medicated outpatients with schizophrenia (SZ). Demographically matched control (CO) subjects (n=16) will only participate in the affective modeling and social and cognitive assessments but not in VR training (see Human Subjects section for details). To determine the optimal dose of VR training, it is necessary to conduct a valid assessment for social functioning pre- and post- treatment. Details of assessments are outlined below. Optimal dose of physiology-based, adaptive VR intervention is unknown but Tsang & Man reported that just ten 30-minute sessions of conventional, non-adaptive VR training was sufficient to obtain an improvement in SZ. In our study, we will examine the effects of social VR training on social and cognitive measures, pre- and post-treatment. At baseline (t1), the PI's will use stratified randomization to assign SZ to two dose conditions: high vs. low. Stratified randomization is used to ensure that potential confounding factors (e.g. age, gender) are evenly distributed between groups. If possible, we will try to match the two groups on IQ, and the Social Functioning Scale, a broad measure of social functioning, but if it cannot be done, we will statistically adjust for them when we test for treatment effects. Everybody will train twice a week but the low dose group will train for 30 mins and the high dose group for 2 x 30 mins per visit. VR task performance will be recorded at each visit. At t1, social, cognitive and symptom assessments will be conducted. The research staff who administer assessments are blind to the group assignment and SZ are unaware which group they are in. The research assistants who supervise VR sessions will NOT conduct assessments because they will be aware of the dosing. After t1, subjects play the VR game for 2.5 weeks, at which point (t2), we repeat the social, cognitive and symptoms assessments plus a satisfaction survey. Then they train for another 2.5 weeks. At 5 weeks (t3), we repeat the assessments and the satisfaction survey. The behavioral measures have been used in intervention trials to be reliable across time with minimal practice effects, or offer alternate forms. The satisfaction survey will solicit user feedback to improve our protocol in the future.

**VR Training:** SZ will play the "Day Out" game in the lab. Biosensors and eye tracking will be used. To boost adherence, we will call/text 2 hours before the visit. They will be paid after each visit and receive a bonus upon reaching the next level of difficulty in the game, and when they complete the training.

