### **Social Assessments:**

(1) **Social Functioning Scale (SFS)** has 79-items with 7 subscales: social engagement, interpersonal communication, daily living activities, recreation, social activities, independent living and employment. Raw scores of the subscales are

converted to scaled score ( $m=100$ ,  $SD=15$ ). **(2) Social Emotional Task from CogState** (SET-CS) is a facial emotion recognition task within CogState (see below). **(3) Bell Lysaker Emotion Recognition test (BLERT)**. Subjects view 10s vignettes of an actor talking about life. After each vignette, subjects select one emotion that was portrayed. There are 3 different stories portrayed in 7 emotions (21 total). Correct responses are summed. **(4) Revised Eyes Test (EYES)** assesses the theory of mind. It asks subjects to decide the mental state of a person from an image of his/her eyes. For each set of eyes, subjects select one word out of 4 choices that best describes what the person in the picture is thinking or feeling. There are 36 trials. These measures were selected for their validity, reliability, and coverage of important domains of social functioning. Our VR game simulates and exercises social interactions, thus, targeting emotion recognition (BLERT, EYES, SET-CS), and theory-of-mind (EYES, BLERT). Practicing these skills will likely lead to broad, beneficial consequences for social functioning (SFS).

**Cognitive Assessments:** **(1) Wechsler Abbreviated Scale of Intelligence (WASI)** will estimate IQ at t1. It will not be repeated at t2 or t3. Baseline IQ may interact with the efficacy of social interventions. **(2) CogState** is a computerized, standardized battery for assessing cognitive abilities ([cogstate.com](http://cogstate.com)). It reliably detects cognitive changes over time, and shows minimal practice effects with repeated administrations. It is widely used to measure cognition in treatment trials. Results are automatically scored. It takes 30 minutes.

**Clinical Symptoms:** SAPS and SANS will be used to measure the severity of symptoms in SZ.

**Satisfaction Survey:** To obtain feedback about VR experience, we will give a 9-item survey that asks about difficulties, hurdles, enjoyment and motivational factors, and solicits suggestions.

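### Allocation is in the investigators' hands, with discretionary matching on IQ and SFS and no stated concealment, so selection bias is not excluded; adjustment for these variables also depends on whether matching works

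*Combined protocol and SAP*

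**What the plan says.** The PROTOCOL section says that, at baseline (t1), "the PI's will use stratified randomization to assign SZ to two dose conditions". Its stated purpose is balance: "Stratified randomization is used to ensure that potential confounding factors (e.g. age, gender) are evenly distributed between groups". Age and gender are thus only examples, and no cut-points, block size or method of generating the sequence follow.

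The same section then adds a second process: "If possible, we will try to match the two groups on IQ, and the Social Functioning Scale". No procedure or tolerance is given for this matching. The fallback is that "if it cannot be done, we will statistically adjust for them when we test for treatment effects".

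Both matching variables are collected at the time point of assignment. The WASI "will estimate IQ at t1" (Cognitive Assessments), and the SFS is one of the social assessments made at t1. The order of steps within t1 is not stated.

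The blinding text covers the assessors and the patients, and keeps those who supervise VR sessions away from assessment. It says nothing about the people who assign.

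The DATA ANALYSIS PLAN compares the doses by a linear mixed model and by an ANCOVA with the pre-treatment value as covariate.

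**The concern.** Two separate weaknesses follow.

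**Allocation.** Randomisation protects the dose comparison only if whoever enters a patient cannot foresee or choose the next arm. Here the investigators carry out the assignment, and a discretionary attempt at matching is added while the matching variables may already be known. If matching is done without a random element by someone who sees earlier assignments, the next arm can often be predicted. A judgement about the patient that is never recorded, such as likely tolerance of longer sessions, could then influence who goes where. Adjusting for IQ and SFS cannot remove that.

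**Analysis.** Whether IQ and SFS enter the model depends on whether matching is judged to have failed, and no criterion for failure is given. If matching is judged successful and they are left out, the analysis ignores variables on which the allocation was balanced.

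The stakes are the main conclusion. The 16 controls receive no training, so high versus low dose is the only randomised contrast. The DATA ANALYSIS PLAN also says that drop-out will help to set the dose and duration for the next phase, so steering by expected tolerance would affect that decision too.

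**Working it through.** The plan gives no alpha, power, effect size or allocation error to reproduce. It mentions power calculations without showing them, and the sample size of 40 has no derivation. What follows is illustration, with assumptions marked.

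**Inputs from the PROTOCOL section:** 40 randomised patients, two arms, assignment at t1, IQ and SFS measured at t1.

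**Assumptions:** 1:1 allocation (20 per arm; the ratio is not stated) and a two-sided 5% test.

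**Step 1. How predictable is the next arm?** This was simulated with 2,000 trials per scenario. Matching and minimisation use four two-level factors; blocked schemes use four strata from two factors. The assigner knows the method and all past assignments. Steering of size *b* means that patients entered when the high arm is the likelier one have an unmeasured prognosis better by *b*/2 SD, and those entered when the low arm is likelier have one worse by *b*/2. There is no true effect, and the test is an unadjusted t-test.

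| Scheme | Guessed correctly | Type I error, b = 0.25 | Type I error, b = 0.5 |
|---|---|---|---|
| Simple randomisation | 50% | 5% | 5% |
| Blocks of 4, four strata | 69% | 5% | 9% |
| Blocks of 2, four strata | 74% | 7% | 11% |
| Minimisation, 80:20 | 76% | 8% | 12% |
| Deterministic matching, four factors | 91% | 9% | 23% |

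Under deterministic matching about 83% of assignments are fixed outright by the patient's characteristics and past assignments. With no steering (*b* = 0), every scheme gives 4 to 6%. So matching on measured variables is not itself the source of bias; foresight combined with steering is. Minimisation is also no less guessable than blocking to someone who knows all past assignments, so the protection has to come from concealment.

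**Step 2. What does leaving out IQ and SFS cost when matching has worked?** Take an outcome SD of 1 and assume that IQ and SFS each correlate 0.4 with outcome and are uncorrelated with each other.

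- Unadjusted SE: √(2/20) = 0.316.
- Variance explained by the two variables: 0.4² + 0.4² = 0.32.
- Adjusted SE: √(0.68 × 2/20) = 0.261.

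Simulation of matched allocation with correlations of 0.4 gives 0.31 without adjustment and 0.27 with it. The unadjusted test rejects about 3.4% of the time instead of 5%: balancing shrinks the true variation of the arm difference, while the residual variance still contains IQ and SFS. In variance terms, (0.31/0.27)² = 1.32.

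**The case against.** The strongest reply is that the plan says randomisation, and means it. A reader might infer that later assignments are made by hand from known patient characteristics. The text does not say so: assignment is by stratified randomisation, and matching is only to be attempted if possible. The words would also cover extra strata, randomised matched pairs, or minimisation with a random element. Nor do the documents say that the investigators recruit patients or see earlier assignments. This stands, and it limits the point to what is unspecified.

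A reader might also argue that stratifying on age, gender, IQ and SFS together would leave too few patients per stratum. The plan does not propose that. It names age and gender as examples of stratification factors and treats IQ and SFS separately. Two two-level factors give four strata of 40/4 = 10 patients on average.

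The wish for balance is reasonable. Taking the stated scaled-score SD of 15 and 20 patients per arm, the SE of an SFS difference is 15 × √(2/20) = 4.7 points, and simple randomisation would give a gap above 7.5 points about 11% of the time.

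Finally, part of the problem is already handled. The ANCOVA always adjusts for baseline SFS when SFS is the outcome, and each outcome's own baseline will absorb some of what IQ and SFS explain, so the gain in Step 2 would be smaller on top of it. What remains is that nothing closes off foresight at allocation, and that adjustment for IQ (and for SFS with other outcomes) is conditional.

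**Conclusion.** The concern holds in a limited form. Investigators assign, matching is discretionary, its variables are measured at the same time point as assignment, and no algorithm, random element or concealment is described for it. Selection bias in the only randomised contrast is therefore not excluded. The documents do not show that it will occur.

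The possible size runs from none (4 to 6% type I error without steering) to about 23% for the worst case examined: deterministic matching on four factors, full knowledge of past assignments and steering of 0.5 SD. Those settings are assumptions. A reader might want a bias in SD units. Steering 10 to 30% of assignments on a trait correlated 0.3 to 0.5 with outcome would give about 0.05 to 0.24 SD (share × 1.596 × correlation). That assumes perfect sorting at the trait median and no reduction by ANCOVA, and the documents support neither those shares nor those correlations, so it is no estimate for this trial.

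Conditional adjustment is a defect that needs no steering. Its direction is conservative: a standard error too wide (0.31 against 0.27 SD with assumed correlations of 0.4) and a type I error of about 3.4%. It costs precision in a 40-patient trial and leaves the model to be chosen after balance has been seen.

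**What to change.** 1. Replace investigator assignment and discretionary matching with one prespecified, computer-run rule that contains a random element. Stratified blocks on age and gender would do, as would minimisation that adds IQ and SFS. State the strata or factor levels, block sizes or assignment probability. A team member who neither enrols nor assesses patients should run it and release the arm only after the patient is irrevocably entered. This separation matters more than which rule is chosen.
2. Include the stratification variables, IQ and baseline SFS as fixed covariates in the dose comparison, in both the ANCOVA and the mixed model, whatever the observed balance. Delete the condition that ties adjustment to failed matching.

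The cost is a short script, a reassigned task and a few degrees of freedom. If minimisation is used, t1 IQ and SFS must be scored before assignment. The documents do not list all staff roles, so it is an assumption that someone on the existing team can take this on.

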## **DATA ANALYSIS PLAN**

Does the VR intervention elicit significant pre-post change on the targeted social attention, measures of social functioning (SFS, SET-CS, BLERT, EYES) and clinical symptoms (SAPS and SANS)? What are the specific treatment parameters that provide the optimal benefit when cost-benefit and other considerations are taken into account? To address training effects on the social assessments, we will use a linear mixed effects model (LMM) analytic approach because it allows for maximally flexible modeling of effects and parameters and for a principled treatment of missing data. To address this question, we will conduct repeated measures LMM analyses. Specific contrasts will directly assess: **1)** The linearity of the slope of change within each group; **2)** Pairwise differences among time points within each group; and, **3)** Group differences in linearity and pairwise differences. Because our power calculations indicate that the most powerful tests of group differences will be provided by an ANCOVA framework (with pre-treatment values serving as the covariate), we will also use this analytic approach to compare the two dose conditions. Although it is important to minimize Type 2 errors in an initial study, we will also generate multiplicity-corrected p values across the 5 primary measures using simulation-based approaches. A similar approach will be used to analyze the clinical symptom and other measures (e.g., CogState) although a generalized linear mixed effects (GLMM) model may be needed to accommodate non-normal distributional properties of the measures. With a particular emphasis on the set of social measures,

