we will also conduct analyses that assess effects on the set as a whole. Depending on the correlational structure of the measures, we will either: **1)** Form 1 or 2 linear composites using prior findings on the dimensional structure of the measures and our own analyses; or **2)** Conduct a multivariate analysis of variances using the flexible facilities of mixed-effects software to accommodate such models. We will assess clinically meaningful change by comparing the post-treatment SZ and normative distribution for each group. To provide a more fine-grained assessment of the proximal effects of training we will assess change over days on the VR task measures (e.g., # of difficulty levels mastered) to assess the rate of learning across, within, and between the dose conditions. Generalized linear and generalized nonlinear mixed effects models will be used to carefully assess the functional form of change over time using several approaches: **a)** Polynomial growth models; **b)** Penalized spline analyses; and, **c)** Non-linear mixed effects models directly estimating parameters particularly relevant to learning. It is important that analyses also address missing data and attrition because: (1) Minimization of drop-out is one of the goals of the VR intervention and will be an important determinant of the dose and duration to use in the R33 phase; and (2) To minimize biases, it is important to use a principled approach to the treatment of missing data on the other outcome measures. We will: (1) Conduct logistic regression and, if feasible, discrete survival analyses predicting drop-out based on weekly data; (2) Use pattern-mixture models and related approaches to estimate treatment effects in the presence of drop-out and assess how different patterns of attrition might moderate effects; and, (3) Try to include in models auxiliary variables that predict drop-out. Supplementary analyses will also test whether performance changes during the training phase mediate the effects of the intervention conditions on social functioning and symptom measures.

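### Dose comparison: fix a short covariate list in advance instead of adjusting for IQ and SFS only when matching fails, and include the randomisation strata (minor)

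*Combined protocol and SAP*

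**What the plan says.** The PROTOCOL section randomises 40 patients to a high or a low dose with stratification: "Stratified randomization is used to ensure that potential confounding factors (e.g. age, gender) are evenly distributed between groups". Age and gender appear only as examples; there is no final list of strata and no age cut-point. The investigators will also try to match the groups on IQ and SFS, "but if it cannot be done, we will statistically adjust for them when we test for treatment effects". No tolerance, test, decision-maker or time point defines a failed match.

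The DATA ANALYSIS PLAN compares the doses in two ways. The linear mixed model (LMM) has contrasts for "Group differences in linearity and pairwise differences", with no covariates named. For ANCOVA, "with pre-treatment values serving as the covariate", the plan adds that "we will also use this analytic approach to compare the two dose conditions". The only other covariates mentioned come under missing data, where the team will try to "include in models auxiliary variables that predict drop-out". No model contains the stratification factors.

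Because the SFS ANCOVA already includes baseline SFS, the gap is limited to IQ and the strata for every outcome, and baseline SFS for outcomes other than SFS.

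**The concern.** The rule leaves covariates out exactly when the groups are balanced on them. Balance removes the covariate's contribution to the true sampling error of the dose difference. If the covariate is not in the model, however, its variance stays in the residual, so the reported standard error is too large and the test rejects too rarely. The same holds for any prognostic factor that was balanced by stratification and then omitted.

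The plan states its priority in the sentence beginning "Although it is important to minimize Type 2 errors in an initial study". With about 20 patients per arm, an avoidable loss of sensitivity runs against that priority. In addition, the model that will be fitted depends on an undefined judgement about whether matching worked.

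**Working it through.** **Inputs.** From the documents: 40 randomised patients, with the outcome's own baseline as the ANCOVA covariate. Assumed, because the documents do not give them: 1:1 allocation (20 per arm), two-sided 5% per measure, complete data unless stated, and all prognostic strengths. The plan mentions power calculations but prints no figures, so there is nothing to reproduce. Below, remaining variance means outcome variance left after the outcome's own baseline, scaled to 1.

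**1. Does the missing criterion matter?** The difference in means of a standardised covariate has SE = √(2/20) = 0.316. The chance that it exceeds 0.25 SD is P(|z| > 0.25/0.316 = 0.79) = 0.429. For at least one of two independent covariates it is 1 − (1 − 0.429)² = 67%. For 0.5 SD: P(|z| > 1.58) = 0.114, and 1 − (1 − 0.114)² = 21% (22% in simulation). Without successful matching, one reasonable cut-off would therefore trigger adjustment in about two trials in three, and another in about one in five.

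**2. How conservative is the baseline-only test after successful matching?** If balanced, omitted factors explain a share q of remaining variance, the true variance of the dose difference is (1 − q) × 2/20, while the model reports about 2/20. With 40 − 3 = 37 degrees of freedom the critical value is 2.026, so the actual type I error is about P(|t₃₇| > 2.026/√(1 − q)).

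| q | 2.026/√(1 − q) | Type I error, formula | Simulated |
|---|---|---|---|
| 0 | 2.026 | 5.0% | 5.0% |
| 5% | 2.079 | 4.5% | 4.4% |
| 10% | 2.136 | 3.9% | 4.0% |
| 20% | 2.265 | 2.9% | 3.0% |
| 30% (IQ and SFS 20%, strata 10%) | 2.422 | 2.0% | 2.4% |

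The simulation used 20,000 trials per cell and allocation within age-by-gender strata, redrawn until both group differences (IQ, SFS) were below 0.2 SD. This is close balance rather than exact balance, so small departures from the formula are expected. The model with the fixed list (baseline, IQ, SFS, two strata terms) stayed at 4.6% to 5.3%.

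**3. What does the fixed list do to power?** Same setting, outcome other than SFS, true difference 0.9 residual SD. Change in points against the baseline-only ANCOVA:

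| Strata explain | IQ and SFS explain 0% | 5% | 10% | 20% |
|---|---|---|---|---|
| 0% | −1.1 | +0.7 | +2.4 | +5.7 |
| 5% | +0.6 | +2.2 | +4.1 | +7.3 |
| 10% | +2.5 | +3.8 | +5.5 | +8.8 |

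A separate simulation gave about −0.7 to +8. For SFS itself, with IQ explaining 0/5/10% and the strata nothing, the change is −0.4/+1.2/+2.7.

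**4. If matching is not achieved** and the plan's rule is applied with a cut-off of 0.25 or 0.5 SD, type I error stays at 3.1% to 5.2%. With IQ and SFS explaining 20% and the strata nothing, power is 83.0% or 80.4% depending on the cut-off, against 84.5% with the fixed list.

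**5. Downside when no covariate is prognostic.**
- Strata balanced by the randomisation: a loss of about 1 to 2 points (2.4 with 20% drop-out, 16 per arm).
- Extra terms unbalanced: 4.0 to 4.5 points at 40 patients.
- Extra terms unbalanced and 32 patients analysed: 5.2 points with matching, 6.8 without.

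On another scale, assuming a baseline correlation of 0.7, the difference detectable with 80% power rises from 0.66 to 0.70 SD with four useless extra covariates (about 6%). Break-even is near 12% of remaining variance for four covariates and 6% for IQ and SFS alone.

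**6. The mixed model.** With complete data, t1 as a response and free group means at t1, the group contrast in t1 to t3 change is the raw difference in change scores. In one check both were −0.294, while ANCOVA gave −0.433. Time-constant covariates do not move this contrast (0.0175 with and without them in another data set), whereas covariate-by-time terms do (−0.0516). These checks show what each model estimates; they do not measure power.

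**The case against.** The strongest defence is that the harm is small and the benefit unproven. Matching uses t1 values, so its success could be judged before any outcome is seen. The power change runs from a loss to a gain depending on prognostic strength, which the documents do not report, and nothing in them shows that break-even is reached. All of this stands, although the plan does not say when the judgement is made. It limits the point to a minor one and rules out promising a power gain.

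It is also fair to say that the adjustment rule refers to tests of treatment effects in general, so it can be read as covering both the LMM and the ANCOVA. A reader might infer that the two analyses will carry different covariates; the text leaves that open but does not establish it.

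A reader might also infer that the conditional rule inflates false positives. A fixed mechanical trigger does not; its error is at or below nominal. Even free choice of the smaller of the adjusted and unadjusted p values gave only about 5.9% with non-prognostic covariates, and the plan does not propose that.

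Finally, the remark under Cognitive Assessments that IQ may interact with efficacy concerns effect modification. It is not evidence that IQ predicts the outcome beyond its baseline.

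What the defence does not remove is that the stated rule drops a covariate in the circumstances where dropping it makes the standard error too wide, and that the strata are in no model.

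**Conclusion.** The point holds as a minor, cheap improvement. The certain gain is a reproducible model that does not turn on an undefined judgement. The possible gain is in power: from about −1 point if nothing is prognostic to about +8 to +9 points if IQ and SFS explain 20%, and the strata 10%, of remaining variance. This assumes 20 per arm, complete data, balanced strata, independent IQ and SFS, and a difference of 0.9 residual SD. The figures apply to the ANCOVA only; no gain has been shown for the LMM.

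Two stronger conclusions are not supported: that the dose comparison is biased or anti-conservative, and that adjustment will necessarily raise power. Nor should a reader assume that having t1 among the LMM responses already adjusts for baseline; with free group means at t1 it does not.

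**What to change.** In the PROTOCOL section, keep the matching clause and replace only the conditional ending with: *and, whatever the balance achieved, the ANCOVA dose comparisons will adjust for the baseline value of the outcome, IQ, the factors actually used in the stratified randomisation and, for outcomes other than SFS, baseline SFS.* Name those factors, with any cut-points, before outcome data are seen, and keep the list short.

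In the DATA ANALYSIS PLAN, add that the LMM group contrasts use the same set, in one of two forms:
- t1 as a covariate, with t2 and t3 as responses; or
- t1 as a response with group means constrained equal at t1, and the other covariates entered with covariate-by-time terms.

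The cost is a sentence in each section, the work of naming the strata, and a few degrees of freedom. If no covariate is prognostic, the loss of power is about 1 to 2 points with balanced strata, about 4 to 5 with unbalanced extra terms, and possibly 5 to 7 with 20% drop-out as well. IQ, SFS and the strata are all known at t1, so allocation and visits do not change.
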